# 3.2.3 Safety

All safety data will be included in the safety data listings and summary tables will be based on the safety population. Across all treatment cycles summary safety tables

will be presented by the dose received in the study limb in the specified Treatment Cycle. For the fixed dose Treatment Cycle 1 selected tables will also be presented by exact dose received. For analyses over repeat treatments by Treatment Cycle, selected tables will also be presented by total body dose received.

Safety tables will be presented by the treatment groups specified in Section 3.2.1.2.

### *3.2.3.1 Adverse Events*

For AEs, the sponsor will use the latest version of Medical Dictionary for Regulatory Activities (MedDRA) in effect within the sponsor company at the time of database lock.

Adverse events will be recorded from time of informed consent until the end of study and all AEs will be considered for inclusion in the analyses.

All AEs reported during the study will be presented in a listing which will be sorted by subject identifier (subject ID), the AE start and end date, primary system organ class (SOC), preferred term (PT) and verbatim text. TEAEs will be assigned to the last Study Treatment prior to the onset of the AE. The Treatment Cycle, the Study Limb Dose, and the Total Body Dose at which each AE started will be included.

Serious AEs, AEs leading to withdrawal, death, and TEAEs will be flagged in the AE listings.

Listings of all serious adverse events (SAE), AEs leading to withdrawal and deaths reported during the study will also be presented, using the same sort order. Listings of AEs of special interest will also be provided, for remote spread of effects as well as for hypersensitivity reactions.

A TEAE is defined as any AE that occurs during the treatment phase of the study if:

(1) it was not present prior to receiving the first intake of study medication, or

(2) it was present prior to receiving the first intake of study medication but the intensity increased during the treatment phase of the study.

(3) it was present prior to receiving the first dose of study treatment, the intensity is the same but the drug relationship became related during the active phase of the study.

A TEAE that occurs under a particular treatment cycle and worsens in intensity under a different treatment cycle will be considered as treatment emergent under the two treatment cycles. In the event of another occurrence of a TEAE with a change in intensity under a different treatment cycle, the subject will also be counted in that different treatment cycle. A given AE will be assigned to the dose received prior to the onset of the AE in the designated treatment cycle.

Adverse events of special interest (AESIs) for Dysport are TEAEs that suggest a possible remote spread of effect of the toxin or events suggestive of hypersensitivity like reactions. TEAEs due to possible remote spread of the effects of Dysport will be identified using the list of MedDRA PTs compatible with the mechanism of action of BTX-A and based on the recommendations from the Committee for Medicinal Products for Human Use (CHMP) and the Food and Drug Administration (FDA). TEAEs potentially representing hypersensitivity reactions will be identified using the Standardised MedDRA Query (SMQ) (narrow search query) for hypersensitivity reactions. A list of MedDRA PTs, used to identify any potential AESI, is provided in Appendix 8.4 of the SAP.

All TEAEs identified using the search strategy described above will be medically evaluated during the study, before the database lock and unblinding, by the sponsor to identify events which could possibly represent 'remote spread of effect of toxin', or which are suggestive of 'hypersensitivity reactions' due to study treatment administration. Cases will be excluded if they are confounded by presence of alternative clinical etiologies (medical history, concomitant medication or diagnosis which could account for the symptoms); if they are considered to be local effects instead of distant spread as judged by the site of injection; the time period between the last study treatment administration and event onset is not in accordance with the expected mechanism of action; or due to insufficient information/evidence to make an assessment.

In the TLFs, only the final list of AESIs confirmed by the sponsor as "a possible remote spread event" or "hypersensitivity reactions" will be taken into account.

Across all Treatment Cycles 1, 2, 3, and 4 an overall summary table of all AEs will be presented by treatment group for **study limb dose** (administered in the specified Treatment Cycle using the dose groups specified in Section 3.2.1.2), summarising:

- Any AE
- Any TEAE
- Any Non Serious TEAE
- Intensity of TEAEs (Severe, Missing, Moderate, Mild)
- Causality of TEAEs (Related, Unknown/Missing, Not related)
- Causality and intensity of TEAEs (Related and Severe, Related and Missing, Related and Moderate, Related and Mild, Missing and Severe, Missing and Missing, Missing and Moderate, Missing and Mild, Not related and Severe, Not related and Missing, Not related and Moderate, Not related and Mild)
- Any TEAE leading to withdrawal (TEAEWD)
- Any TEAE leading to death
- Any SAEs

In the above table, intensity, causality and causality combined with intensity of TEAEs, subjects will be presented in all the categories of intensity and causality in which their TEAE(s) have been reported.

Presentation by study limb dose will also include overall summary of all AEs for all treatment cycles combined.

In addition to the above, the following TEAE summary tables will be presented by treatment group for **study limb dose** across all treatment cycles (using the dose groups specified in Section 3.2.1.2 as administered in the specified Treatment Cycle):

- TEAEs with the number and percentage of subjects and the number of occurrences presented by primary SOC and PT
- TEAEs by intensity with the number and percentage of subjects and the number of occurrences by primary SOC and PT
- TEAEs by causality with the number and percentage of subjects and the number of occurrences by primary SOC and PT
- TEAEs by causality combined with intensity with the number and percentage of subjects and the number of occurrences by primary SOC and PT

- SAEs with the number and percentage of subjects with SAEs and the number of occurrences by primary SOC and PT
- SAEs by intensity with the number and percentage of subjects and the number of occurrences by primary SOC and PT
- SAEs by causality with the number and percentage of subjects and the number of occurrences by primary SOC and PT
- SAEs by causality combined with intensity with the number and percentage of subjects and the number of occurrences by primary SOC and PT
- TEAEWDs with the number and percentage of subjects with TEAEWDs and the number of occurences by primary SOC and PT
- TEAEWDs by intensity with the number and percentage of subjects and the number of occurrences by primary SOC and PT
- TEAEWDs by causality with the number and percentage of subjects and the number of occurrences by primary SOC and PT
- TEAEWDs by causality combined with intensity with the number and percentage of subjects and the number of occurrences by primary SOC and PT
- Non serious TEAEs by treatment group, with the number and percentage of subjects with non serious TEAEs and the number of occurrences presented by primary SOC and PT, for all non serious TEAEs occurring for  $\geq 5\%$  of subjects in at least one treatment group at the PT level
- TEAEs by treatment group, with the number and percentage of subjects with TEAEs and the number of occurrences presented by primary SOC and PT, for all TEAEs occurring for  $\geq 3\%$  of subjects and more than 1 subject in at least one treatment group at the PT level

If a subject experiences more than one TEAE within a category (PT or primary SOC) the subject will be counted only once in that category.

In the summary of TEAEs by intensity and causality, in the event of multiple reports of the same PT for a subject, the maximum intensity (severe>missing >moderate>mild) and the most serious causality (related>not related) will be counted.

For all AESIs the following selected tables will be produced **by study limb dose group** across all treatment cycles 1, 2, 3, and 4:

- Overall summary table of all AESIs
- AESIs with the number and percentage of subjects and the number of occurrences presented by primary SOC and PT
- AESIs by causality combined with intensity with the number and percentage of subjects and the number of occurrences by primary SOC and PT.

## TEAEs for fixed dose Treatment Cycle 1

In addition to the TEAE summary tables by study limb dose described above (including Treatment Cycle 1), the following tables will be produced by study limb dose group for those subjects who received the **exact dose in the study limb** (see Section 3.2.1.2). These tables will be provided for (TE)AEs at Treatment Cycle 1.

- Overall summary table of all AEs
- TEAEs with the number and percentage of subjects and the number of occurrences presented by primary SOC and PT

- TEAEs by intensity with the number and percentage of subjects and the number of occurrences by primary SOC and PT
- TEAEs by causality with the number and percentage of subjects and the number of occurrences by primary SOC and PT
- TEAEs by causality combined with intensity with the number and percentage of subjects and the number of occurrences by primary SOC and PT
- SAEs with the number and percentage of subjects with SAEs and the number of occurrences by primary SOC and PT
- TEAEWDs with the number and percentage of subjects with TEAEWDs and the number of occurrences by primary SOC and PT
- TEAEs by treatment group, with the number and percentage of subjects with TEAEs and the number of occurrences presented by primary SOC and PT, for all TEAEs occurring for  $\geq 3\%$  of subjects and more than 1 subject in at least one treatment group at the PT level.

### AESIs for fixed dose Treatment Cycle 1

In addition to the AESI summary tables by study limb dose (including Treatment Cycle 1), the following tables will be for those subjects who received the **exact study limb dose**. These tables will be provided for AESIs at Treatment Cycle 1.

- Overall summary table of all AESIs
- AESIs with the number and percentage of subjects and the number of occurrences presented by primary SOC and PT
- AESIs by causality combined with intensity with the number and percentage of subjects and the number of occurrences by primary SOC and PT.

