## 1.2 Study Design

This is a phase III, multicentre, double blind, prospective, randomised, controlled multiple treatment study. Subjects will receive a maximum of four treatments over the course of a minimum of one year's study participation.

At study entry, subjects will be randomised into one of the following three treatment groups for Treatment Cycle 1:

- Group A: Dysport 16 U/kg in one upper extremity (the study limb).
- Group B: Dysport 8 U/kg in the study limb.
- Group C: Dysport 2 U/kg in the study limb.

Randomisation will be in a 1:1:1 ratio. Stratification will be performed according to age range (2 to 9 years and 10 to 17 years) and BTX (Botulinum Toxin) naïve or non-naïve status assessed at baseline.

For Treatment Cycles 2, 3 and 4, subjects are planned to receive Dysport 8 U/kg or 16 U/kg according to the treatment allocation by the IRS and will remain double blind throughout the study. However, it is possible that subjects will not receive the planned treatment as dose adaptations (reduction or increase) will be possible based upon the Investigator's judgements regarding safety and efficacy. The total dose for the study limb must not exceed 320 U in the 8 U/kg group and 640 U in the 16 U/kg group.

The planned retreatment interval is 16 weeks and a maximum of four treatments will be administered.

At study entry, a primary targeted muscle group (PTMG), either the elbow flexors or wrist flexors, will be nominated by the Investigator. The PTMG can be changed for subsequent treatments, from elbow to wrist flexors or wrist to elbow flexors, provided that the following criteria are fulfilled:

- The Modified Ashworth Scale (MAS) score of the other muscle group not selected for the last treatment (new PTMG) must be higher than the last treatment PTMG, and
- The new PTMG must have a modified MAS score of greater or equal to 1+.

For Treatment Cycles 2, 3 and 4, injection into the lower extremity/extremities and the nonstudy upper limb will be allowed at the same time as the study limb is injected.

The stages of the study and the planned doses for the study are provided in Figure 1.

Figure 1 Planned Study Structure and Dose Modifications Available During the Study

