#### Injection

All treatments

After each treatment administration, the follow up visit schedule is as follows:

- Week 2 (telephone call, safety follow up).
- Week 4 (telephone call, safety follow up).
- Week 6.
- Week 12 (telephone call, safety follow up).
- Week 16.

At Week 16, subjects will be assessed for their eligibility to receive the next treatment. Subjects who are eligible for retreatment will be given the next treatment. Any subjects not eligible for retreatment will be evaluated every 6 weeks  $\pm 2$  weeks in additional visits until they are eligible for retreatment.

Each subject will participate in the study for approximately 1 year to 1 year and 9 months depending on the number of treatments administered and the treatment intervals. The duration of the follow up period will be dependent upon the treatment interval as follows:

• All subjects whose first three treatment intervals fall between  $\ge 16$  and  $\le 22$  weeks will receive four treatments and will exit the study as soon as a new

injection is required and no later than 22 weeks after last injection (up to a maximum of 1 year and 9 months' study duration).

• All other subjects will not be given any further study treatment after Week 52 and will exit the study after 16 weeks of follow up of the last treatment.

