#### **3 STATISTICAL METHODS**

#### 3.1 Statistical Analysis Strategy

The statistical analyses will be performed in accordance with ICH E9 guideline [1] and will be based on the pooled data from the individual study sites, unless otherwise stated.

Statistical analyses will be performed by a Contract Research Organisation CC, under the supervision of the Sponsor's statisticians.

Overall, the analysis strategy is to evaluate efficacy and safety data from the initial fixed dose Treatment Cycle 1, where only the study limb could be treated. In addition efficacy and safety over repeated treatments will be evaluated, using analyses by Treatment Cycle, as described below.

Baseline for all analyses, including by Treatment Cycle, is defined as the last value prior to the initial Study Treatment 1 on Day 1.

#### Fixed dose Treatment Cycle 1

For assessment of efficacy and safety of Dysport 8 or 16 U/kg for the treatment of upper limb spasticity, relative to the minimal dose of 2 U/kg, Treatment Cycle 1 will be evaluated in which a fixed dose was administered to the designated study limb.

Data will be analysed according to the randomised dose (efficacy) or actual dose received (safety) for the study limb in Treatment Cycle 1.

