#### SAP Final Version 2.0: 19 Oct 2018

# 3.1.6 Significance Testing and Estimation

## Fixed Dose Treatment Cycle 1

Apart from tests described in section 3.1.5, all statistical tests performed on the fixed dose Treatment Cycle 1 efficacy endpoints will be conducted, unless otherwise specified, at a two-tailed  $\alpha$  level of 0.05 and each tested Dysport dose group (8 U/kg and 16 U/kg) will be compared to Dysport 2 U/kg separately. Statistical tests will be performed on the efficacy endpoints for Treatment Cycle 1, up to Week 16 (inclusive), no statistical tests will be performed for any additional visits of Treatment Cycle 1 (any visits after Week 16).

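### Cycle 1 adverse event tables by dose run to the next injection with no time limit, so unequal retreatment intervals would make the crude percentages compare unequal observation windows

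*SAP*

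**What the plan says.** - **Assignment of events.** SAP 3.2.3.1: "TEAEs will be assigned to the last Study Treatment prior to the onset of the AE". Neither that section nor the visit windows in SAP 3.2.14 set a latest onset day for a Cycle 1 event.
- **Length of Cycle 1.** SAP 1.2: "The planned retreatment interval is 16 weeks and a maximum of four treatments will be administered". Children not eligible at Week 16 are seen about every 6 weeks "in additional visits until they are eligible for retreatment". The outer limit for those with long intervals is "All other subjects will not be given any further study treatment after Week 52".
- **Measure.** The AE tables in SAP 3.2.3.1 give numbers and percentages of subjects and numbers of occurrences. SAP 3.2.15 takes all subjects in the population as denominator. The visible text plans no rate per exposure time, although SAP 3.2.13.11 derives Cycle 1 exposure.
- **Role of Cycle 1.** On efficacy and safety of the two tested doses, SAP 3.1 says: "relative to the minimal dose of 2 U/kg, Treatment Cycle 1 will be evaluated in which a fixed dose was administered". SAP 1.2.1, Table 1, moves Group C to 8 or 16 U/kg from Cycle 2, so no later cycle has a planned 2 U/kg group. Additional exact-dose tables are also specified: "These tables will be provided for (TE)AEs at Treatment Cycle 1".
- **Related outputs.** SAP 3.2.9.2 reports the length of Cycle 1 by dose group. SAP 3.2.3.1, under repeat treatment, tabulates TEAEs by days since the last injection, with bands ending at Day 112 and Day 140.

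**The concern.** The time for which a child's events count towards Cycle 1 is fixed after randomisation, by when that child becomes eligible for retreatment. Suppose one dose group is retreated later than another. Its children stay in Cycle 1 longer and collect more background childhood events there. In the group retreated earlier, events in the same calendar weeks are moved to Cycle 2 and to the dose given then.

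A crude percentage then mixes the effect of dose on harm with the effect of dose on time to retreatment. Longer intervals at the tested doses would make those doses look worse than they are. Shorter ones would make them look better. This matters because Cycle 1 is the only cycle in which the tested doses are set against 2 U/kg.

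**Working it through.** The plan gives no figure on this point to reproduce, so this is a sensitivity calculation.

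**Inputs from the documents:** earliest planned retreatment at 16 weeks and nominal later visits at 22 and 28 weeks (SAP 1.2); 70 children per arm (SAP 1.3.4).

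**Assumptions:** the split of retreatment times, the 16-week risk, and the same hazard in both groups. The documents give none of these.

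**Formulas.** With share p_k of children having window w_k:
- Mean window = Σ p_k·w_k.
- Share of events after Week 16 at a constant rate = 1 − 16/mean.
- Percentage with at least one event = Σ p_k·[1 − exp(−λ·w_k)], with λ = −ln(1 − R)/16 and R the 16-week risk.

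For R = 50%, λ = 0.0433 per week, and the risk by Weeks 16, 22 and 28 is 50.0%, 61.4% and 70.3%.

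| Assumed split at Weeks 16/22/28 (%), 2 U/kg v tested dose | Mean window (weeks) | Events after Week 16 | Subjects with an event | Spurious gap |
|---|---|---|---|---|
| Equal: 60/30/10 in both | 19.0 v 19.0 | 15.8% v 15.8% | 55.5% v 55.5% | 0 |
| Mild: 85/10/5 v 70/20/10 | 17.2 v 18.4 | 7.0% v 13.0% | 52.2% v 54.3% | 2.2 points |
| Middle: 90/8/2 v 60/30/10 | 16.7 v 19.0 | 4.3% v 15.8% | 51.3% v 55.5% | 4.1 points |
| Strong: 95/5/0 v 40/40/20 | 16.3 v 20.8 | 1.8% v 23.1% | 50.6% v 58.6% | 8.1 points |

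Worked example, middle row: 0.90 × 50.0 + 0.08 × 61.4 + 0.02 × 70.3 = 51.3, against 0.60 × 50.0 + 0.30 × 61.4 + 0.10 × 70.3 = 55.5 (gap 4.1 before rounding). Exchanging the two splits reverses the sign of each gap.

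**Rare events.** With R = 3%, the risk by Weeks 16, 22 and 28 is 3.0%, 4.1% and 5.2%. The mild, middle and strong gaps become 0.2, 0.4 and 0.8 points. The middle gap is 3.1% v 3.5%, about 0.3 of a child in 70.

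**Early clustering.** Let a share f of the 16-week cumulative hazard H = ln 2 = 0.693 fall in Weeks 0 to 4, and let the later rate (1 − f)·H/12 per week continue after Week 16. With f = 75% the three gaps are 0.8, 1.6 and 3.0 points. With f = 90% they are 0.3, 0.6 and 1.3 points.

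**Do the remedies work?**
- With a common 16-week window, equal hazards give 50.0% v 50.0% in every row.
- With a constant hazard, events per subject-week equal λ in both groups, because expected events are λ × mean window.
- With early clustering, a rate alone over-corrects. For f = 90% and the middle split, the later rate is 0.1 × 0.693/12 = 0.00578 per week. Expected events per child are 0.693 + 0.72 × 0.00578 = 0.697 over 16.72 weeks and 0.693 + 3.00 × 0.00578 = 0.711 over 19.00 weeks. The rates are 0.0417 and 0.0374 per week, a ratio of 0.90. The rate and the common window therefore belong together.

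**The case against.** A reader might infer that the higher doses will show an artificial excess because their effect lasts longer, and that the SAP expects this since its section 5 plans a Kaplan-Meier analysis of time to retreatment by treatment group. The documents do not support that. Summaries by treatment group are the SAP's default (3.2), so this one does not signal an expected difference. Protocol 4.3 says that effect can persist to 16 weeks in lower limb studies and gives no comparison by dose. The detailed reinjection criteria are blacked out, so being ineligible cannot be equated with still responding.

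Other points on this side also stand:
- SAP 3.1.6 restricts hypothesis tests on efficacy to Week 16. SAP 3.2.2.5 still describes later Cycle 1 efficacy visits. The safety tables are descriptive (Protocol 11.4.4), so an uncapped safety table breaks no rule of the plan and no type I error is at stake.
- Cycle 1 safety is grouped by actual dose, with cut-offs at 6 and 12 U/kg (SAP 3.2.1.2), so it is not strictly a comparison of randomised arms.
- Special interest events are less exposed. SAP 3.2.3.1 drops cases whose timing does not fit the mechanism or that have another explanation, which should remove many late background events.
- The middle gap is about 3 children in 70, against a standard error of about 8 points for a difference between two such percentages.

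The tables in SAP 3.2.9.2 and the onset bands answer the concern only in part. They show that windows differ and when TEAEs start. But no at-risk denominator is stated for the bands, and a child with events in two bands cannot be counted once by adding subject percentages. If occurrences are also shown, those can be added through Day 112. No such banding is stated for SAEs or withdrawals. The table index is blacked out, so further outputs cannot be ruled out.

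**Conclusion.** The point holds as a conditional weakness. The AE window in Cycle 1 is uncapped and set after randomisation, and the main measure is a crude percentage of all subjects. If retreatment intervals differ by dose group, TEAE, SAE and withdrawal percentages are distorted in the direction of the difference.

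The figures of about 2 to 8 points rest on assumed splits, a constant hazard and a 50% 16-week risk. They illustrate what could happen and predict nothing about this trial. The distortion is zero with equal intervals. It is under 1 point for events with 3% risk, and about 1 point or less when nearly all the hazard falls in the first 4 weeks. Common background events carry most of it; early toxin-related events are little affected. It warrants a cheap addition to the SAP. It does not warrant replacing the planned tables.

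**What to change.** In SAP 3.2.3.1, keep the full-cycle tables and add for Cycle 1, by dose group:

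1. Exposure-adjusted event rates for TEAEs, SAEs and TEAEs leading to withdrawal, using the Cycle 1 exposure already derived in SAP 3.2.13.11.
2. The overall AE summary, and the TEAE and SAE tables by SOC and PT, restricted to onset from injection to Day 112, or to retreatment or withdrawal if earlier. Day 112 is already a boundary of the planned onset bands. It lies inside the SAP's Week 16 visit window of Days 99 to 127, so a footnote should say that the limit is an onset day and not the Week 16 visit.
3. In the time-since-injection table, the number of children still at risk in each band.

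The cost is a few extra tables with an onset filter. No new data, visits or changes to treatment are needed. Events after Day 112 stay visible in the full-cycle tables.

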10.1.4 Adverse Events of Special Interest

The effects of Dysport and all BTX products may spread from the area of injection to produce symptoms consistent with BTX effects. These symptoms have been reported hours to weeks after injection. Remote spread of toxin that affects swallowing and breathing can be life threatening, and there have been reports of death. The risk of symptoms is increased in subjects who have underlying conditions (e.g. disorders of the neuromuscular junction) that would predispose them to these symptoms. Dysport is contraindicated in individuals with known hypersensitivity to any BTX preparation or to any of the components in the formulation. Adverse events of special interest (AESIs) for Dysport are AEs that suggest a possible remote spread of effect of the toxin or hypersensitivity. A list of preferred terms of AESIs is provided in the Statistical Analysis Plan. All AEs will be monitored by the sponsor to determine if they meet the criteria of AESIs. These AESIs will be further analysed to determine if there is a plausible possibility that they represent distant spread of toxin or hypersensitivity. In order to perform the analysis, variables including alternate aetiology (medical history, concomitant medication, or diagnosis which could account for the symptoms), location of Dysport administration, and temporal relationship to Dysport administration will be considered by the sponsor.

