#### **Safety**

If a value required a retest (for laboratory values, vital signs and ECG) the closest non-missing reliable value to the scheduled visit will be used in the summary tables. An assessment will be considered reliable if it is performed without any technical problem and if the result is within the range of plausible values.

For adverse events with missing information for the intensity and causality the value will not be replaced and will be summarised as a separate category.

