## 3.2.4.2 Missing or Incomplete Dates

In all listings, missing or incomplete dates should be left as they have been recorded. However, for calculation/sorting/assignation based on dates, the following methods will be used:

- (1) The most conservative approach will be systematically considered (i.e. if the onset date of an AE/concomitant medication is missing/incomplete, it is assumed to have occurred during the study treatment phase (i.e. a TEAE for AEs) except if the partial onset date or the stop date indicates differently).
- (2) Similarly, if the onset time of an AE is missing then a conservative approach will again be taken, so that it is assumed to be a TEAE unless the onset date, stop date, or stop time indicates differently.
- (3) A missing/incomplete date of medical history or disease diagnosis will be assumed to have occurred before any study treatment.
- (4) A medication with partial start and stop dates will be considered as concomitant treatment, except if the partial dates indicate differently.
- (5) Where this is possible, the derivations based on a partial date will be presented as superior inequalities (i.e.: for an AE started in FEB2004 after the administration performed on 31JAN2004, the days since last dose will be "≥2", similarly the duration of ongoing AEs or medication will be "≥xx" according to the start and last visit dates).
- (6) If an AE or SAE onset date is partial or missing, the event will be allocated to the first treatment where onset could have occurred (taking into account date and time stopped).
- (7) If the start date of a medication is partial or missing, the medication will be assigned to the most recent treatment received on or before the medication start date (taking into account date stopped).

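### Potential AESIs that cannot be assessed are dropped from the AESI outputs, so those tables do not separate 'not assessable' from 'ruled out'

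*SAP*

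**What the plan says.** Protocol 10.1.4 states that AESIs "are AEs that suggest a possible remote spread of effect of the toxin or hypersensitivity". It then has the sponsor analyse them further, to judge whether distant spread or hypersensitivity is plausible, considering "variables including alternate aetiology (medical history, concomitant medication, or diagnosis which could account for the symptoms), location of Dysport administration, and temporal relationship" to injection.

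SAP 3.2.3.1 puts this into operation in three steps.

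1. TEAEs are searched with a preferred-term list for remote spread (SAP 8.4) and the narrow standardised MedDRA query for hypersensitivity.
2. Every hit is "medically evaluated during the study, before the database lock and unblinding, by the sponsor". A case is removed for an alternative cause, for being a local effect, for timing that does not fit the mechanism, "or due to insufficient information/evidence to make an assessment".
3. "In the TLFs, only the final list of AESIs confirmed by the sponsor as" a possible remote-spread event or a hypersensitivity reaction is used. The affected outputs begin with the "Overall summary table of all AESIs" and include the AESI tables by system organ class and preferred term, and by causality with intensity.

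For other missing AE information the SAP has different rules. Where intensity or causality is missing, "the value will not be replaced and will be summarised as a separate category" (SAP 3.2.4.1, Safety). For missing or partial dates, "The most conservative approach will be systematically considered", so an event with unknown onset is taken as treatment emergent unless other information shows otherwise (SAP 3.2.4.2).

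**The concern.** Three of the four grounds for removal are findings against an AESI: another cause, a local effect, or the wrong timing. The fourth is not a finding. If the information is insufficient, the event is as possible after review as before it, and possibility is how both documents define an AESI. Removing it turns absence of evidence into a negative classification.

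Long-term safety is the secondary objective (Protocol 3.2), and Protocol 10.1.4 says that remote spread affecting swallowing or breathing can be life threatening. A reader of the AESI tables will want to know whether a zero or a low count means that candidates were examined and rejected, or that some could not be examined. As planned, the tables cannot answer that.

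**Working it through.** The documents state no AESI rate, no number of unassessable cases and no precision target for AESIs, so there is no figure of the plan's to reproduce. The check is mainly a comparison of texts.

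**Texts side by side**

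| Missing item | Treatment | Effect on the event |
|---|---|---|
| AE intensity or causality (SAP 3.2.4.1) | Separate category | Kept and visible |
| AE onset date (SAP 3.2.4.2) | Assumed treatment emergent unless contradicted | Kept |
| Information to assess a candidate AESI (SAP 3.2.3.1) | Case removed | Not in AESI outputs |

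- Protocol 10.1.4 names alternative cause, location and timing as variables to consider. Its list is open-ended, but it does not provide for removal for lack of information.
- The visible part of SAP section 5 (changes from protocol) does not mention this added ground.
- Protocol 10.1.2 reserves the not-related category for cases with enough evidence to rule causality out. Protocol 10.3.3 asks for a provisional causality opinion when SAE information is incomplete. Nothing visible in SAP 3.2.3.1 prevents removal of an event that the investigator rated as related.

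**Direction**

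Let c be the confirmed and u the unassessable subjects in a group of n. The planned table shows c/n. With unassessable cases kept it would show (c + u)/n. Since u ≥ 0, the rule can only lower the count of possible AESIs.

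**Illustration, with assumed counts**

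Take n = 70, the planned number randomised per group (SAP 1.3.4); AESI tables will use dose actually received, so denominators may differ. Limits are exact (Clopper-Pearson) 95%. For x = 0 the upper limit is 1 − 0.025^(1/70) = 5.13%. For x ≥ 1 it is the 0.975 quantile of Beta(x + 1, n − x).

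| Assumed confirmed, unassessable | Table as planned | If unassessable are kept |
|---|---|---|
| 0, 1 | 0/70, upper limit 5.13% | 1/70 = 1.43%, 0.04% to 7.70% |
| 0, 2 | 0/70, upper limit 5.13% | 2/70 = 2.86%, 0.35% to 9.94% |
| 0, 3 | 0/70, upper limit 5.13% | 3/70 = 4.29%, 0.89% to 12.02% |
| 2, 2 | 2/70 = 2.86%, 0.35% to 9.94% | 4/70 = 5.71%, 1.58% to 13.99% |

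For all 210 subjects, 0/210 has an upper limit of 1.74% and 1/210 one of 2.62%.

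**Illustration, with an assumed rate**

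Suppose a proportion p of subjects have a true AESI and a share f of those cannot be assessed. The tabulated rate is p(1 − f), and the chance that a group of 70 shows at least one is 1 − (1 − p(1 − f))^70.

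- p = 2%: with nothing removed, 1 − 0.98^70 = 0.757. With f = 10% the tabulated rate is 1.8% and the chance 0.720. With f = 50% these are 1.0% and 1 − 0.99^70 = 0.505.
- p = 5%: 0.972 with nothing removed; 0.960 at f = 10% (rate 4.5%) and 0.830 at f = 50% (rate 2.5%).
- p = 8%: 0.997 with nothing removed; 0.995 at f = 10% (rate 7.2%) and 0.943 at f = 50% (rate 4.0%).

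The rule matters most where events are rare. The values of p and f are assumptions, not estimates.

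**The case against.** The other side has several sound arguments.

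- **Nothing disappears from safety reporting.** A removed case stays in the full AE listing, with its cycle and dose, and in the TEAE tables by organ class and term. This stands. A reader might infer that missing evidence is counted as no event at all; the documents do not support that. The event loses its AESI label only.
- **The candidates can be rebuilt.** Partly true: SAP 8.4 lists the remote-spread terms. But term rows cannot be added to give subjects, because one subject can appear under several terms. The hypersensitivity terms are not listed, and even a rebuilt list would not show why a case was removed.
- **The bar for entry is low, and review is planned.** This stands. The sponsor confirms a possible event, not a proven one, and Protocol 10.1.4 foresees narrowing by review. Only the insufficient-information ground is new.
- **Review takes place before unblinding.** This also stands. A reader might infer that the rule favours a dose group; nothing in the documents shows that.
- **The true rate need not be biased downwards.** The search list includes constipation, hemiparesis and muscular weakness, and Protocol 2.1 describes weakness and hemiplegia as features of cerebral palsy. Some unassessable hits will not be toxin effects, so counting all of them could overstate the rate. This is why a separate category is better than simple inclusion.
- **Few cases may be affected.** Investigators must obtain adequate information on every AE (Protocol 10.2), and incomplete data are queried (Protocol 13.4). That may keep the number small, but it does not make it visible.
- **A further output may exist.** The table and listing indexes are blacked out, so a table of all hits cannot be excluded. The SAP's restriction of the outputs to the final confirmed list argues against one.

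**Conclusion.** The point holds for the AESI outputs. SAP 3.2.3.1 sets a rule under which an unassessable candidate is tabulated like a rejected one. That sits badly with an AESI definition based on possibility and with the SAP's own handling of missing AE information. The count of possible AESIs can only fall as a result.

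Three limits apply. The events remain in general safety reporting. The documents do not establish a downward bias in the true AESI rate, or any bias between dose groups. The numerical effect is unknown: the 5.1% against 7.7% contrast in a group of 70 assumes that exactly one case was removed and none confirmed.

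This should be corrected before unblinding. It concerns reporting and does not invalidate the safety analysis.

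**What to change.** Amend SAP 3.2.3.1 so that insufficient information is an outcome of the sponsor's review in its own right and no longer a reason for exclusion. Report by dose group:

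- (a) all search-identified events, separately for remote spread and hypersensitivity;
- (b) events the sponsor confirms as possible AESIs;
- (c) events that could not be assessed;
- (d) events excluded, by reason.

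Add a sensitivity summary that counts (c) together with (b) as AESIs. The main AESI tables can stay on (b), provided (c) is shown beside it. Record the classification before unblinding, as already planned, and give subjects as well as occurrences.

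The cost is a wording change in the SAP and added rows in the AESI summary tables. These exist by study limb dose, by exact dose in Cycle 1 and by total body dose, so the rows recur across several tables. No new data are needed and no clinical procedure changes. The AESI rate may look slightly less favourable.
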